## Section 2: Introduction

### Background and rationale

Gout is an increasingly common disorder characterized by elevated serum urate (SU) and by acute and chronic arthritis causing severe disability and pain. Long-term management of gout focuses on urate-lowering therapy (ULT) and keeping SU under its solubility threshold. When SU is kept under the threshold for solubility, the frequency of gout flares will decrease, and the urate crystals dispositioned in the joints will dissolve. New therapeutic management of gout has in recent years emerged. However, despite the potential for effective treatment, gout management remains suboptimal. According to the overarching principles, and latest EULAR recommendations - emphasizing the need to address comorbidities - in the management of gout, every person with gout should be systematically screened for associated comorbidities and cardiovascular risk factors, including kidney impairment, coronary heart disease, heart failure, stroke, peripheral arterial disease, smoking, hyperlipidemia, hypertension, diabetes, and obesity. Appropriate management of these comorbidities is an integral part of the management of gout.

Epidemiological data link obesity and other components of the metabolic syndrome to the development of gout. Both conditions share pathogenetic mechanisms and the development of one disease increases the risk of the other and may trigger the onset of a vicious circle. In addition, insulin resistance (IR) has been closely connected to gout. Insulin stimulates the renal tubular sodium hydrogen exchanger facilitating secretion of hydrogen and reabsorption of not only sodium, bicarbonate, and chloride but also organic anions such as urate. This constitutes a putative mechanism by which IR and hyperinsulinemia cause hyperuricemia. However, the hypothesis that a beneficial effect of weight loss in these patients is caused by a change in insulin resistance is currently controversial. Hypertension and dyslipidemia as part of the metabolic syndrome has been linked to gout. Epidemiological studies support the alleged association between SU and hypertension and find that uric acid is an independent risk factor for developing hypertension. Consistency is found in a large number of prospective observational studies. Gout has also been associated with both increased very-low-density lipoprotein (VLDL) triglycerides as well as low levels of high-density lipoprotein (HDL)-cholesterol. In hyperuricemic individuals there is also a strong linear relation between, total cholesterol, triglycerides, LDL cholesterol and apolipoprotein-

B levels and an inverse relationship with HDL and SU. A causal link between gout and hypertension/gout and dyslipidemia has yet to be discovered.

There is some physiological evidence, although sparse, that weight loss in patients with gout reduces both SU and number of gout flares. Despite the scarcity of data regarding the effects of weight loss in gout, international guidelines recommend dietary intervention and weight loss as a core management strategy in patients with concomitant gout and obesity. Medical treatment strategies have focused on either treatment of the acute inflammatory response of flares or long term reduction of SU by either inhibiting its production with xanthine oxidase inhibitors or increase renal excretion with uricosuric agents. To date, no treatment strategy has targeted the basic dysmetabolic mechanisms linking obese patients with gout.

The Parker Institute has previously designed and applied a well-documented weight loss program running over 16 weeks (CAROT study) that effectively results in a significant weight loss (average ~12% of body weight) in obese (body mass index [BMI] >30 kg/m^2) patients with knee osteoarthritis with beneficial improvements in knee pain and function

## Aims

To explore the short term clinical and laboratory effects related to a rapid diet-induced weight loss in obese individuals with gout compared to an unblinded control group. The aim with the current study is to address whether obese gout patients are able to reduce their body weight, leading to a reduction in SU levels, with an improvement in pain and fatigue. We will also explore whether there are any significant adverse events related to an intensive weight loss program in these individuals.

## Hypotheses

The group undergoing the intensive diet will lose more weight than the group that “only” follow the conventional diet. The weight loss will mediate lower urate levels which will improve the clinical outcomes in these individuals.

## Objectives

Primary efficacy objective: To compare the effect of intensive weight loss, relative to the control group, on changes in body weight from baseline to week 16, in patients with gout and concomitant obesity.

Key secondary efficacy objectives: To compare the effect of intensive weight loss, relative to the matched control group, on changes in serum urate, changes in VAS-fatigue, and changes in VAS-Pain from baseline to week 16, in patients with gout and concomitant obesity.

Other secondary objectives: To explore the effect of the intensive weight loss, relative to the matched control group, on all the following exploratory secondary outcomes:

- proportion of participants maintaining serum urate levels <6mg/dL at visit week 8 and week 16
- percentage reduction in serum urate (%) at final visit (week 16)
- the proportion of individuals with any gout flare in the FIRST 8 weeks following randomization
- the proportion of individuals with any gout flare in the LAST 8 weeks following randomization
- the number of gout flares during the trial period for each patient (up to week 16)
- change in functional status (HAQ) from baseline to week 16
- change in patient global (VAS) from baseline to week 16
- change in swollen joint count (SJC) from baseline to week 16
- change in tender joint count (TJC) from baseline to week 16
- change in number of tophi from baseline to week 16
- change in 36-Item Short Form Health Survey SF-36: Mental Component Scale (MCS) from baseline to week 16
- change in 36-Item Short Form Health Survey SF-36: Physical Component Scale (PCS) from baseline to week 16.

## Section 3: Study Methods

### Trial design

The study was designed as a 16 (8+8) week pragmatic proof-of-concept randomized, non-blinded, parallel-group trial. Treatment allocation was a 1:1 ratio. Patients were randomized to either 16 (8+8) weeks of low-energy diet (LED; 3.4 MJ/day; i.e., the Intensive Diet [ID] group) *OR* a corresponding 16-week with guidance on how to live with conventional hypo-energetic, high protein diet (app. 5 MJ/day) defined as a control group (i.e., conventional diet [CD] group).

## Randomization

After baseline measurements, the participants were randomized to either Intensive Diet (ID) or Conventional Diet (CD) group. A computer-generated randomization sequence was produced, before any participants were enrolled, allocating participants in permuted blocks of 2 to 4 to the ID or the CD group (1:1). The randomization sequence was prepared using SAS Proc Plan; after the list was generated it was concealed in a password-protected computer file only accessible by the data manager. Randomization was stratified according to sex (M vs F), baseline obesity class (<40 vs.  $\geq 40$  kg/m^2), and SU level (< 6 vs.  $\geq 6$  mg/dL). These eight mutually independent randomization sequences (each including 60 “virtual patients”) was entered into the eCRF by the data manager ([name]).

## Power and sample size

Using SAS Power and Sample Size (Copyright © 2013 by SAS Institute Inc., Cary, NC, USA) it was calculated assuming that the standard deviation (SD) of weight change at week 16 would be 6.0 kg, that, 60 patients (30 in each group) would provide 89% confidence (power=0.888) to detect a clinically relevant 5 kg difference (p=0.05, two-sided) in mean bodyweight change between individuals allocated to intensive or conventional diet. If a drop-out rate of up to 20% (i.e., 6 patients in each group) is assumed, the trial will still have an acceptable power (>0.80) to detect a 5 kg difference between the groups.

Among the key secondary outcome measures is the mean change in SU at the final visit: Assuming a common SD of 1.6 mg/dL, a total sample size of 60 gout patients (randomized 1:1) will have a sufficient statistical power (81.5%) to detect a mean difference of 1.2 mg/dL. Patient-Reported Outcome Measures (PROMs; e.g. VAS-Pain and VAS-fatigue): With 60 patients in total, the trial will have sufficient power to detect a statistically significant effect size (i.e. standardized mean difference [SMD]) corresponding to a large clinical effect (SMD=0.8; power=86.1%).

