## Section 4: Statistical Principles

### Confidence intervals and P values

All analyses will be analyzed and reported as two-sided, done at a 5% significance level. Statistical tests will be conducted between the intensive weight loss and control group for the pre-defined primary and key secondary endpoints in a hierarchical manner. Thus gatekeeping procedure using serial testing will be applied to adjust for multiplicity among the key secondary outcomes. Formal statistical testing will be performed, in a prespecified sequence, as presented below, until one of the key secondary endpoints in the hierarchy fail to be statistically significant at  $\alpha=0.05$ . To limit the risk of type 1 errors we have selected only four endpoints to test - the primary endpoint and three key secondary endpoints. This procedure will preserve the “Family Wise Error Rate” of the

multiple analyses. The analyses will be performed in sequence until one of the analyses has failed to show the significant difference or all analyses have been completed at a significance level of 0.05. The sequence of the analyses for the selected secondary efficacy endpoints are listed as: (1) Change in body weight; (2) Change in serum urate; (3) Change in VAS Fatigue. (4) Change in VAS Pain.

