### Analysis methods

For the primary and key secondary outcomes, we will use analysis of covariance (ANCOVA) modelled using repeated-measures mixed linear model analysis. Statistical tests inferring from P-values will be performed in sequence until one of the analyses has failed to show the significant difference or all analyses have been completed at a significance level of 0.05. The sequence of the analyses for the selected secondary efficacy endpoints are listed as: (1) Change in body weight; (2) Change in serum urate; (3) Change in VAS Fatigue. (4) Change in VAS Pain. The statistical model will include diet group (ID/CD) and time (in weeks) as fixed effects, and the interaction between time and diet group, with the respective variable (e.g. body weight at baseline) as covariate. Furthermore, the possible impact of the factors used for the stratified randomization will be explored, i.e. sex (M/ F), obesity class (<40/≥40 kg/m^2), and SU level (< 6/≥6 mg/dL) but will not be considered part of the primary model. We aim to assess whether data provide evidence of superiority of ID to CD group (primary objective). Thus, the null hypothesis is no difference

between treatments at endpoint (week 16). Response variables and adverse events (binary outcomes) will be analyzed by comparing the proportions responding in each group with the Risk Difference (and 95% CI's), with no further adjustments for covariates.

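### The 86.1% power quoted for VAS pain and VAS fatigue is a stand-alone figure; under the SAP's testing order, and on the same unadjusted basis, it is at most 81.5%

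*SAP*

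**What the plan says.** The SAP's Power and sample size section gives three power figures, each for 60 patients randomised 1:1 and a two-sided 5% test:

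- **Body weight:** 0.888 for a 5 kg difference with SD 6.0 kg. With up to 20% drop-out (6 per arm), "the trial will still have an acceptable power (>0.80) to detect a 5 kg difference between the groups".
- **SU:** "a total sample size of 60 gout patients (randomized 1:1) will have a sufficient statistical power (81.5" per cent), for a difference of 1.2 mg/dL with SD 1.6 mg/dL.
- **Patient-reported outcomes:** "Patient-Reported Outcome Measures (PROMs; e.g. VAS-Pain and VAS-fatigue): With 60 patients in total, the trial will have sufficient power", quantified as 86.1% for a standardised mean difference of 0.8.

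Under Objectives, the key secondary comparisons are "changes in serum urate, changes in VAS-fatigue, and changes in VAS-Pain from baseline to week 16". Under Confidence intervals and P values, the order of testing is "1) Change in body weight; (2) Change in serum urate; (3) Change in VAS Fatigue. (4) Change in VAS Pain", and formal testing continues "until one of the key secondary endpoints in the hierarchy fail to be statistically significant". Analysis methods repeats the rule: "Statistical tests inferring from P-values will be performed in sequence until one of the analyses has failed to show the significant difference". The model named there is a repeated-measures mixed model "with the respective variable (e.g. body weight at baseline) as covariate".

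The protocol's section on power and sample size has the same figures. It does not name the two VAS scales in that sentence, and it sets no testing order.

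**The concern.** The SAP took the protocol's power figures unchanged, attached the 86.1% to VAS pain and VAS fatigue by name, and separately placed these two outcomes third and fourth in a fixed sequence. A stand-alone power ignores that sequence. SU stands ahead of both outcomes and is planned at a smaller standardised effect (1.2/1.6 = 0.75, against 0.80), so it limits how often either can be tested formally at all.

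What is at stake is interpretation. If SU narrowly misses significance, fatigue and pain get no formal test. A reader holding the 86.1% figure would think those comparisons had a better chance of a formal positive result than the plan gave them.

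**Working it through.** **Inputs (SAP, Power and sample size; Confidence intervals and P values).** Two-sided alpha 0.05; n = 30 per arm; standardised effects d: weight 5/6.0 = 0.833, SU 1.2/1.6 = 0.75, patient-reported outcomes 0.80. Order: weight, SU, fatigue, pain, each tested at 0.05 only if all earlier tests succeed.

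**Step 1: reproduce the stated figures.** For an unadjusted two-sample t-test, the noncentrality is d × √(n/2) with 2n − 2 degrees of freedom. At n = 30, √15 = 3.873 and the critical value (58 df) is 2.002.

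| Outcome | Noncentrality | Power | SAP |
|---|---|---|---|
| Weight | 0.833 × 3.873 = 3.23 | 0.8876 | 0.888 |
| SU | 0.75 × 3.873 = 2.90 | 0.8150 | 81.5% |
| Patient-reported, 0.8 | 0.80 × 3.873 = 3.10 | 0.8614 | 86.1% |

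All three match. They are therefore single-test powers, unadjusted for baseline, with every patient evaluable.

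**Step 2: apply the testing order.** Fatigue is formally positive only if weight, SU and fatigue are all significant. The probability of a joint event cannot exceed that of any one of its parts:

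P(weight, SU and fatigue all significant) ≤ min(0.8876, 0.8150, 0.8614) = 0.8150.

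The same bound holds for pain. It needs no assumption about correlation between outcomes. Against the quoted figure the gap is at least 86.1 − 81.5 = 4.6 percentage points.

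**Step 3: how far below the bound.** The documents give no correlations between outcomes, so these values are illustrative. Under independence:

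- fatigue: 0.8876 × 0.8150 × 0.8614 = 0.623
- pain: 0.623 × 0.8614 = 0.537

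With an assumed equal pairwise correlation, simulation of 100,000 trials gave the following.

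| Assumed correlation | Fatigue | Pain |
|---|---|---|
| 0.3 | 66.4% | 60.3% |
| 0.5 | 69.5% | 64.9% |
| 0.8 | 75.4% | 73.1% |

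**Step 4: the drop-out case on the same basis.** At 24 per arm, √12 = 3.464 and the critical value (46 df) is 2.013. Noncentralities are 2.89, 2.60 and 2.77, giving weight 80.7%, SU 72.0% and patient-reported outcomes 77.4%. The weight result confirms the SAP's statement. The SAP gives no figure for the other two.

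**The case against.** The strongest objection is that 81.5% is the power of a test the SAP does not plan to use. The main analysis adjusts for the baseline value. Suppose the correlation between baseline and week 16 is 0.5 (an assumption; the documents give none). If 1.6 mg/dL is the SD of the week-16 value, the residual SD is 1.6 × √(1 − 0.25) = 1.386, so d = 1.2/1.386 = 0.866. SU power is then about 91% at 30 per arm and 84% at 24 per arm. If 1.6 is the SD of the change, the result at this correlation is the same, because √(2 × (1 − 0.5)) = 1 makes the two SDs equal. This stands. A reader might infer that formal power for fatigue and pain can never exceed 81.5% in this trial. The documents do not support that: the limit holds on the SAP's own power basis, not for the planned model. What remains under any model is that the formal tests of fatigue and pain are limited by the SU power, whatever that is.

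A second objection is that the SAP never presents 86.1% as power under the sequence. Table 2 plans a 95% confidence interval for each outcome. On the stated inputs and basis, 86.1% is still the chance that the fatigue or pain interval excludes zero, whatever happens to SU. This also stands. The figure is correct as a stand-alone power and lacks only that label.

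A third concerns drop-out. A reader might infer that the SAP wrongly claims adequate power for SU and patient-reported outcomes after 20% loss. It does not: it ties both to 60 patients and applies the 0.80 threshold after drop-out to the 5 kg weight difference only. Nor do the documents show that power would be below 80% in that case, given the adjusted model and its use of week-8 data from patients who leave later.

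**Conclusion.** The point holds as a minor inconsistency within the SAP. It names VAS pain and VAS fatigue for a power of 86.1%, while its testing order gives them a formal test only after weight and SU succeed. On the basis that produced the figure (unadjusted t-tests, 60 evaluable patients, SU 1.2 mg/dL with SD 1.6, standardised difference 0.8), formal power for either is at most 81.5%. It would be 62.3% for fatigue and 53.7% for pain if the outcomes were independent.

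The bound rests on the planned SU effect. At 30 per arm it would rise to 86.1% only with a true SU difference of 0.80 × 1.6 = 1.28 mg/dL. Baseline adjustment may raise all these powers by an unknown amount. The drop-out values for SU and patient-reported outcomes are useful context and show no error. Primary power and type I error control are not affected.

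**What to change.** In the SAP's Power and sample size section, add after the SU and patient-reported figures:

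> The values 81.5% and 86.1% are stand-alone powers of unadjusted two-sample t-tests with all 60 patients evaluable. On that same basis, power for the formal tests of VAS fatigue and VAS pain is at most 81.5%, because they are tested only after SU is significant. The planned baseline-adjusted mixed model may give higher power for all these endpoints, by an amount that depends on the correlation between baseline and week 16, which is not specified here; 81.5% is therefore not an absolute ceiling for the planned analysis.

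Optionally, for consistency with the body-weight check:

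> With 24 patients per arm the unadjusted stand-alone powers are 72.0% for SU and 77.4% for patient-reported outcomes.

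The cost is a few sentences and a less favourable stated power for two key secondary endpoints. Sample size, testing order, alpha, models and planned tables do not change.

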## Framework

The trial aims to explore if an intensive diet is superior to a conventional diet regarding weight loss in a group of obese gouty arthritis patients.

## Timing of final analysis

Final analysis is done after all patients have been included and finished the trial (after last-patient last-visit), and after full approval of this SAP by the investigators.

## Timing of outcome assessments

The schedule of study procedures included is given in the table below.

| VARIABLE                                   | Screening
(approx. -2
wks) | Baseline
(0 wks) | Intermediate
(8 wks) | Endpoint
(16 wks) |  |
|--|----------------------------------|---------------------|-------------------------|----------------------|--|
| Secretariat:                        |                                  |                     |                         |                      |  |
| Information                                |                                  |                     |                         |                      |  |
| Motivational appraisal                     |                                  |                     |                         |                      |  |
| Eligibility criteria/Screening (phone)     | X                                |                     |                         |                      |  |
| Demographics and clinical features: |                                  |                     |                         |                      |  |
| Age, years                                 |                                  | X                   |                         |                      |  |
| Male, y/n                                  |                                  | X                   |                         |                      |  |
| Ethnicity, n (%)                           |                                  | X                   |                         |                      |  |
| Duration of gout, years                    |                                  | X                   |                         |                      |  |
| Height, cm                                 |                                  | X                   |                         |                      |  |
| Body mass index, kg/m          |                                  | X                   | (X)                     | (X)                  |  |
| Flares* in the preceding year, count       |                                  | X                   |                         |                      |  |
| Presence of palpable tophi, y/n            |                                  | X                   | X                       | X                    |  |
| Comorbidities:                      |                                  |                     |                         |                      |  |
| History of kidney stones, y/n              |                                  | X                   |                         |                      |  |
| History of gall stones, y/n                |                                  | X                   |                         |                      |  |
| Cardio Vascular Disease, y/n               |                                  | X                   |                         |                      |  |
| Diabetes, y/n                              |                                  | X                   |                         |                      |  |
| Hypertension, y/n                          |                                  | X                   |                         |                      |  |
| Hyperlipidaemia, y/n                       |                                  | X                   |                         |                      |  |
| Urate Lowering therapy:             |                                  |                     |                         |                      |  |
| Allopurinol, y/n                           |                                  | X                   |                         |                      |  |
| Febuxostat y/n                             |                                  | X                   |                         |                      |  |
| Probenecid y/n                             |                                  | X                   |                         |                      |  |
| Benzbromarone, y/n                         |                                  | X                   |                         |                      |  |
| Anti-inflammatory prophylaxis:      |                                  |                     |                         |                      |  |
| NSAIDs, y/n                                |                                  | X                   |                         |                      |  |
| Prednisone, y/n                            |                                  | X                   |                         |                      |  |
| Colchicine y/n                             |                                  | X                   |                         |                      |  |
| Concurrent medication:              |                                  |                     |                         |                      |  |
| Diuretics y/n                              |                                  | X                   |                         |                      |  |
| Aspirin y/n                                |                                  | X                   |                         |                      |  |
| Antihypertensive medication y/n            |                                  | X                   |                         |                      |  |

|   |  |   |   |   |
|---|--|---|---|---|
| Lipid lowering agents y/n                                 |  | X |   |   |
| Diabetes medication y/n                                   |  | X |   |   |
| Blood tests (lab. work):†                          |  |   |   |   |
| Creatinine, mg/dL   |  | X | X | X |
| eGFR, mL/min/1.73m                            |  | X | X | X |
| Serum urate, mg/dL  |  | X | X | X |
| Physical examination (Nurse):                      |  |   |   |   |
| Flares* in the last 8 weeks, count                        |  | X | X | X |
| Body weight, kg   |  | X | X | X |
| Touch screen (PROMs):                              |  |   |   |   |
| SF-36 health survey, score                                |  | X | X | X |
| Activity limitation (HAQ), score                          |  | X | X | X |
| Pain (VAS), mm  |  | X | X | X |
| Patient global (VAS), mm                                  |  | X | X | X |
| Fatigue (VAS), mm   |  | X | X | X |
| Physical examination (MD):                         |  |   |   |   |
| ACR/EULAR gout classification                             |  | X |   |   |
| Gout according to expert opinion                          |  | X |   |   |
| Swollen joint count, 0-66                                 |  | X | X | X |
| Tender joint count, 0-68                                  |  | X | X | X |
| Palpable tophi count                                      |  | X | X | X |
| Randomisation (after confirming written informed consent) |  | X |   |   |
| Harms and adverse events‡ (AEs):                   |  |   |   |   |
| Withdrawal, y/n   |  |   | X | X |
| Withdrawal due to AEs, y/n                                |  |   | X | X |
| Number of serious adverse events, count                   |  |   | X | X |
| Death, y/n  |  |   | X | X |

